4.4 Early Withdrawal of Subjects

4.4.1 When and How to Withdraw Subjects

Patients will be withdrawn from the study prior to study completion if:

1. Subjects elect to withdraw consent
2. Subject is found to be ineligible for the protocol as per the Inclusion/Exclusion criteria.
3. Subjects experience a serious adverse event felt to possibly be related to acamprosate administration as determined by PI and/or DSMB.
4. Failure of the subject to comply with protocol requirements.
5. Exhibition of unacceptable toxicity which would make it difficult or dangerous to comply with further protocol requirements such as study visits, blood draws, etc.
6. There are changes in medical status of the subject such that the Investigator believes that subject safety will be compromised or that it would be in the best interest of the subject to stop participation in the study.

7. Death of the subject.
8. Subjects with a test consistent with pregnancy such as a positive beta-hCG.
9. Subject is lost to follow-up.
10. Any complication that requires prolongation of the hospitalization or change in treatment and in the opinion of the investigator is related to the study drug.

If subjects are withdrawn from the study, they will be replaced to ensure a total of 10 patients complete the study in its entirety. The data collected up until the time of withdrawal from the study will be included in analysis.

Follow up from subjects withdrawn from study treatment will include:

- Clinic visit at time of withdraw from study will be recommended. Beyond risk of returning to alcohol consumption, sudden study treatment termination should not include any subject safety considerations.
- Follow up phone call 3 months after withdrawal from study

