8.1 Definitions

Unanticipated Problems Involving Risk to Subjects or Others (UPIRTSO)

Any unanticipated problem or adverse event that meets the following three criteria:

- Serious: Serious problems or events that results in significant harm, (which may be physical, psychological, financial, social, economic, or legal) or increased risk for the subject or others (including individuals who are not research subjects). These include: (1) death; (2) life threatening adverse experience; (3) hospitalization - inpatient, new, or prolonged; (4) disability/incapacity - persistent or significant; (5) breach of confidentiality and (6) other problems, events, or new information (i.e. publications, DSMB reports, interim findings, product labeling change) that in the opinion of the local investigator may adversely affect the rights, safety, or welfare of the subjects or others, or substantially compromise the research data, **AND**
- Unanticipated: (i.e. unexpected) problems or events are those that are not already described as potential risks in the protocol, consent document, not listed in the Investigator's Brochure, or not part of an underlying disease. A problem or event is "unanticipated" when it was unforeseeable at the time of its occurrence. A problem or event is "unanticipated" when it occurs at an increased frequency or at an increased severity than expected, **AND**
- Related: A problem or event is "related" if it is possibly related to the research procedures.

Adverse Event

An untoward or undesirable experience associated with the use of a medical product (i.e. drug, device, biologic) in a patient or research subject.

Serious Adverse Event

Adverse events are classified as serious or non-serious. Serious problems/events include;

- death
- life threatening adverse experience
- hospitalization
- inpatient, new, or prolonged; disability/incapacity
- persistent or significant disability or incapacity

and/or per protocol may be problems/events that in the opinion of the investigator may have adversely affected the rights, safety, or welfare of the subjects or others, or substantially compromised the research data.

All adverse events that do not meet any of the criteria for serious, will be regarded as **non-serious adverse events**.

Adverse Event Reporting Period

For this study, the study treatment follow-up period is defined as 12 weeks following the last administration of study treatment.

Preexisting Condition

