*** Relationship Index**

The relationship of an AE to the Investigational Drug is a clinical decision by the principal investigator (PI) based on all available information at the time of the completion of the CRF and is graded as follows:

1. Not related: a reaction for which sufficient information exists to indicate that the etiology is unrelated to the study drug; the subject did not receive the study medication or the temporal sequence of the AE onset relative to administration of the study medication is not reasonable or the event is clearly related to other factors such as the subject's clinical state, therapeutic intervention or concomitant therapy.
2. Unlikely: a clinical event, including laboratory test abnormality, with a temporal relationship to drug administration which makes a causal relationship improbable and in which other drugs, chemicals, or underlying disease provide plausible explanations.
3. Possible: a clinical event, including laboratory test abnormality, with a reasonable time sequence to administration of the drug but which could also be explained by concurrent disease or other drugs or chemicals; information on drug withdrawals may be lacking are unclear.
4. Probable: a clinical event including laboratory test abnormality, with a reasonable time sequence to administration of the drug, unlikely to be attributed to concurrent disease or other drugs or chemicals and which follows a clinically reasonable response on withdrawal (de-challenge): re-challenge information is not required to fulfill this definition.
5. Definite: a reaction that follows a reasonable temporal sequence from administration of the drug, or in which the drug level has been established in body fluids or tissues, that follows a known or expected response pattern to the suspected drug, and that is confirmed by improvement on stopping or reducing the dosage of the drug, and reappearance of the reaction on repeated exposure (re-challenge).

Severity Index

The maximum intensity of an AE during a day will be graded according to the definitions below and recorded in details as indicated on the CRF. If the intensity of an AE changes over a number of days, then separate entries should be made having distinct onset dates.

1. Mild: AEs are usually transient, requiring no special treatment, and do not interfere with patient's daily activities.

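### Read literally, section 4.4.1 ends a withdrawn patient's analysed data at withdrawal, which conflicts with the plan's own 12-week adverse event period after the last dose

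*Combined protocol and SAP*

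**What the plan says.** The primary endpoint (section 3.4) is the safety profile as measured by adverse event reporting.

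On withdrawn patients, section 4.4.1 first says that "they will be replaced to ensure a total of 10 patients complete the study in its entirety", and then: "The data collected up until the time of withdrawal from the study will be included in analysis". The listed reasons for withdrawal include item 3, "Subjects experience a serious adverse event felt to possibly be related to acamprosate administration as determined by PI and/or DSMB". Items 5, 6 and 10 are unacceptable toxicity, a change in medical status that compromises safety, and a drug-related complication.

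The same section then lists what happens afterwards. It opens with "Follow up from subjects withdrawn from study treatment will include" and names two contacts: "Clinic visit at time of withdraw from study will be recommended" and "Follow up phone call 3 months after withdrawal from study".

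Section 8.1, under the heading Adverse Event Reporting Period, states that "the study treatment follow-up period is defined as 12 weeks following the last administration of study treatment". Sections 8.1 and 8.2 also have unresolved events followed to resolution or another defined end. The worksheet in 8.3.1 records whether an event resolved after treatment was stopped, and when.

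Section 7.2 bases safety analyses on all subjects, and 7.3 evaluates everyone who took at least one dose. Neither gives a time window.

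**The concern.** The plan collects safety information after withdrawal, but the one sentence on what is analysed stops at withdrawal. An analyst who follows that sentence would leave out an event first reported at the 3-month call, or a worsening within 12 weeks of the last dose.

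The omission would not fall at random. Four of the ten withdrawal reasons (items 3, 5, 6 and 10) are safety reasons, so the shortened records would include those of the patients who tolerated the drug least. In a study of 10 completers, one patient can decide whether a type of event appears in the tables at all. Section 1.1 makes the larger efficacy trial conditional on no safety concerns being identified, so the completeness of those tables matters.

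**Working it through.** **No figure to reproduce.** Section 7.1 states that no power analysis was done, and no dropout rate is given. The check is a comparison of the text, followed by arithmetic for scale.

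**Step 1: what continues after withdrawal, and what the literal sentence does with it.**

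| Source | Continues after withdrawal? | Analysed if 4.4.1 is taken literally? |
|---|---|---|
| Event that began before withdrawal (7.2, 7.3) | – | Yes |
| Its resolution and causality grade (8.3.1, Relationship Index) | Yes; the grade uses all information available when the CRF is completed | Probably, through the grade and resolution field |
| Clinic visit at withdrawal (4.4.1) | On the boundary; recommended only | Unclear |
| New or worsening event within 12 weeks of last dose (8.1) | Yes | No |
| Call 3 months after withdrawal (4.4.1) | Yes | No |

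The conflict therefore concerns new or worsening events after withdrawal. The date of the cut-off is also uncertain, because the analysis sentence refers to withdrawal from the study and the follow-up list to withdrawal from study treatment.

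**Step 2: direction.** With W patients withdrawn and replaced, 10 + W are treated, and 7.3 keeps all of them in the denominator. Leaving out later events can only reduce the numerator or leave it unchanged. This holds for counts of events and for counts and proportions of patients with an event, which suit the descriptive tabulation in 7.2. It need not hold for rates per patient-week, which the plan does not specify.

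**Step 3: share of the window.** Assume that withdrawal and last dose both fall at week w. The defined window is w + 12 weeks, of which a strict cut-off keeps w. Share lost = 12/(w + 12).

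| w | Weeks kept | Window (weeks) | Share lost |
|---|---|---|---|
| 1 | 1 | 13 | 12/13 = 92% |
| 4 | 4 | 16 | 12/16 = 75% |
| 8 | 8 | 20 | 12/20 = 60% |
| 11 | 11 | 23 | 12/23 = 52% |

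**Step 4: chance that something is missed (illustration).** Let q be a patient's risk of a new event in the 12 weeks after withdrawal. The chance of at least one such event among W withdrawn patients is 1 − (1 − q)^W. W and q are assumptions, since the documents give neither.

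| | q = 0.05 | q = 0.10 | q = 0.20 |
|---|---|---|---|
| W = 2 | 10% | 19% | 36% |
| W = 3 | 14% | 27% | 49% |

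**Step 5: effect of one omission (illustration).** Take W = 2, so 12 treated, and a type of event seen in one patient and only after withdrawal. Included, it is 1/12 = 8.3% (exact 95% CI 0.2% to 38.5%). Omitted, it is 0/12 = 0% (0% to 26.5%).

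**The case against.** The strongest reply is that no exclusion is written down. The sentence says what is included, and it comes straight after the replacement rule. It may mean only that replaced patients are not discarded. Sections 7.2 and 7.3 point the same way by keeping every dosed patient.

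A reader might also infer that de-challenge outcomes are lost, and with them the two highest causality grades. The documents do not support this. An event that leads to withdrawal began before it and stays in the analysis. Its grade is not tied to the withdrawal date, and the worksheet has a field for resolution after stopping. 'Definite' further requires the reaction to reappear on re-challenge, which a patient permanently off drug would not normally undergo, so later data would rarely make that grade reachable.

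Nor does the text say that completers are analysed through their whole follow-up. Section 7 sets no window for anyone, and section 6.5 asks only about serious events at the week-24 call.

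The shares in Step 3 are calendar time. Section 4.4.1 schedules one call after withdrawal and no laboratory tests. Some reasons for withdrawal (death, loss to follow-up, withdrawn consent) leave no later data, or only data that need permission under 4.4.2. Finally, this is a descriptive pilot with no hypothesis test.

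All of this stands, and it limits the point to new or worsening events after withdrawal. It does not remove the point. No sentence says that such events are analysed, the most natural reading of 4.4.1 is that they are not, and the primary endpoint depends on which reading is used.

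**Conclusion.** The concern holds in a limited form. The literal wording of 4.4.1 conflicts with the 12-week period and event follow-up in section 8 and with the 3-month call in 4.4.1 itself. Section 7 does not resolve the conflict. New or worsening events after withdrawal could be omitted, selectively because several withdrawal reasons are safety events, and only in the direction of fewer events.

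The size cannot be stated as a bias. A strict cut-off would drop between 52% (week 11) and 92% (week 1) of the defined calendar window, assuming that withdrawal coincides with the last dose. How many events that represents depends on the number withdrawn and their later risk, and the documents give neither.

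Two stronger conclusions should not be drawn. One is that the reported profile will be too favourable: it may be, but only if such events occur and the literal reading is applied. The other is that safety oversight during the trial would miss these events. Recording, follow-up and DSMB review are governed by section 8, and the sentence in 4.4.1 concerns the analysis only.

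**What to change.** Replace the sentence in 4.4.1, and repeat the rule in 7.3, along these lines:

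> All adverse events with onset up to 12 weeks after the last dose, their outcomes, and any laboratory results actually collected in that time enter the safety analysis for every patient who received at least one dose. This includes information from the withdrawal visit and the 3-month call, and is subject to permission after withdrawal of consent. Each item is flagged as before or after the last dose.

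Defining the window by onset matters because 3 calendar months (3 × 365.25/12 = about 91 days) run slightly past 12 weeks (84 days). An event inside the window may first be reported at the call. The rule also gives completers a stated window: with a last dose at week 12, it ends at 12 + 12 = week 24, the time of their final call.

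In 4.4.1, separate withdrawal from study treatment from withdrawal from the study, and say to which the follow-up list and the analysis rule apply. Leave the Relationship Index unchanged.

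The cost is small: no extra contacts, tests or patients, and slightly more tabulation. Some post-treatment events unrelated to the drug will appear, and the flag shows which events came after the last dose. The change should be made before the data are summarised, so that the window is not chosen after the results are known.

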Study duration will be six months. During the study, patients will complete monthly MELD-Na labs and receive a phone call weekly for the first month, then monthly for a total of 3 months. Urine ethyl glucuronide will be done at enrollment and once monthly. Patients will then have a follow up visit at 12 weeks, with labs, urine ethyl glucuronide, vital signs and physical exam. During telephone assessments and at the follow up visit, patients will be asked about potential side effects and hepatic decompensation. Other variables to be collected at enrollment and at the 3 month visit include Child-Pugh score, West Haven grading of HE, vital signs at enrollment and current medications. At enrollment, during phone calls and at the follow up visit, patients will be asked standardized questions to assess for HE based on the abbreviated telephone version of the mini-mental state examination (MMSE). Follow up telephone visits at 13 and 24 weeks will be conducted, primarily to monitor for adverse events and alcohol relapse.

The Pennsylvania Alcohol Craving Scale (PACS) will be applied before treatment initiation, weekly for the first month on treatment, then monthly thereafter. This will include the need severity scale (mild, moderate, severe) at baseline and at each assessment by phone call and in clinic.

Alcohol use relapse will be monitored. Any amount of alcohol use as revealed during follow-up considered a relapse event. Alcohol use will be captured and categorized as none, slip (no longer drinking at most recent follow up) or sustained alcohol use (minimum 100 days drinking). Slips and sustained alcohol use will be categorized as binge drinking, frequent drinking, or both (binge drinking as more than 6 units/day for men and 4 units/day for women and frequent drinking as alcohol use in 4 or more days/week regardless of quantity per day) (Lee et al., 2018).

Basic descriptive statistics and a qualitative analysis will be performed. Analyses will be performed using SPSS 25 (Chicago, IL). Results will not contain any patient-specific information.

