4.4.2 Data Collection and Follow-up for Withdrawn Subjects

If a subject withdraws consent to participate in the study, for subject safety reasons, attempts will be made to obtain permission to collect follow up information whenever possible. Attempt will be made when the patient reports withdrawal of consent.

5 Study Drug

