5.5 Subject Compliance Monitoring

At weekly telephone assessments for the first month, and then monthly telephone assessments and then clinic visit at 3 months, the study team will ask the patient if he or she has missed any acamprosate doses. Subjects will be asked to count their remaining pills and detail how many they were initially prescribed and when. If patients are significantly non-compliant, defined as taking less than 75% of prescribed medication, they will be withdrawn from the study.

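### Patients under 75% adherence, or with certain drug-related events, leave the study and not only the drug, so later craving, alcohol and laboratory data come selectively from those who took and tolerated it

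*Combined protocol and SAP*

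**What the plan says.** Section 5.5 deals with significant non-compliance, "defined as taking less than 75% of prescribed medication, they will be withdrawn from the study". Section 4.4.1 lists failure to comply among the grounds for withdrawal from the study. It also lists a serious adverse event possibly related to acamprosate, a complication judged related to the drug, and "Exhibition of unacceptable toxicity which would make it difficult or dangerous to comply with further protocol requirements".

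On replacement, section 4.4.1 says: "If subjects are withdrawn from the study, they will be replaced to ensure a total of 10 patients complete the study in its entirety". On data use it says: "The data collected up until the time of withdrawal from the study will be included in analysis". The list of remaining contacts then opens with a different term: "Follow up from subjects withdrawn from study treatment will include". That list holds two items: a clinic visit, recommended only, and "Follow up phone call 3 months after withdrawal from study".

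Section 4.4.2 adds that "attempts will be made to obtain permission to collect follow up information whenever possible", but only for patients who withdraw consent. Section 7.3 evaluates everyone who received at least one dose. Section 3.1 classes alcohol use as none, "slip (no longer drinking at most recent follow up) or sustained alcohol use (minimum 100 days drinking").

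**The concern.** Stopping a drug and leaving a study are different events, and the plan gives them one consequence. A patient who takes 70% of the tablets, still consents and can be reached by telephone goes off the schedule of calls, urine tests and blood draws.

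The secondary objective in section 2 is the effect of acamprosate on relapse, measured by PACS and reported alcohol use. Poor adherence and poor tolerance may plausibly go with craving and drinking. If those patients drop out of the schedule, the later weeks describe mainly patients who took and tolerated the drug. In a descriptive study of 10 completers, a few such removals could change the picture that is carried into the planned placebo-controlled trial.

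**Working it through.** The plan states no figure on this point to reproduce, and section 7.1 reports no power analysis. The check is schedule arithmetic.

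**Inputs**
- Schedule table (end of section 6), after baseline: PACS and MMSE at weeks 1, 2, 3, 4, 8, 12, 13 and 24 (8 contacts).
- Same table: urine ethyl glucuronide, and the electrolytes, creatinine, total bilirubin and INR used for MELD-Na, at weeks 4, 8, 12 and 24 (4 each).
- Section 3.1 prose: urine at enrolment, monthly and at the 12-week visit, so weeks 4, 8 and 12 (3 tests). The week 24 urine test appears only in the table. For blood, section 6.5 also asks for final tests at week 24.
- Three-month call: no window is stated. Assumed 84 to 92 days after withdrawal.
- Week 24 = 24 × 7 = day 168; planned treatment = 12 × 7 = 84 days.

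**Assessments missed** (scheduled after the week of withdrawal)

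| Withdrawn just after | Urine, table | Urine, prose | MELD-Na labs | PACS and MMSE |
|---|---|---|---|---|
| Week 1 | 4 of 4 | 3 of 3 | 4 of 4 | 7 of 8 |
| Week 4 | 3 of 4 | 2 of 3 | 3 of 4 | 4 of 8 |
| Week 8 | 2 of 4 | 1 of 3 | 2 of 4 | 3 of 8 |

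For withdrawal just after week 4, the week 8 and week 12 assessments fall inside the planned treatment period. For PACS that is 2 of the 6 contacts planned up to week 12; the other two missed contacts (weeks 13 and 24) are off drug for everyone.

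If the same patient stayed on the schedule, none of these would be missed by design.

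**Secondary illustration: the 100-day category.** Read 100 days as elapsed days from the start of drinking, counted from enrolment (an assumption). The latest start that can still be classed as sustained is the day of last contact minus 100.
- Kept to week 24: 168 − 100 = day 68.
- Withdrawn at day 28: call on day 28 + 84 = 112 to 28 + 92 = 120; latest start day 12 to 20.
- Withdrawn at day 56: call on day 140 to 148; latest start day 40 to 48.
- Withdrawn at day 7: call on day 91 to 99; no start after enrolment qualifies.

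Drinking that begins after withdrawal is seen for at most 84 to 92 days, which is below 100. If it is still going on at the call, it is not a slip either. Kept on schedule, a patient who starts at day 28 has 168 − 28 = 140 days. Withdrawal just after week 4 thus changes the possible class only for drinking that starts between about day 12 to 20 and day 68.

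**The case against.** **The secondary endpoint is on-treatment.** Section 3.5 limits it to cravings and relapse while on acamprosate. Read strictly, drinking after the drug stops lies outside it. This stands as a limit. But section 2 states the objective without that restriction, and section 3.1 uses the week 13 and week 24 calls to monitor relapse off drug. Section 5.5 also does not say that a patient under 75% adherence has stopped the drug, so the removal itself may cut off on-treatment data.

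**The call is not empty.** A reader might infer that the three-month call collects nothing of use. The documents do not support that. Section 8.2 requires adverse-event questioning at every contact, and section 3.1 applies craving questions at telephone assessments. What is missing is a statement that data after withdrawal are analysed: section 4.4.1 commits only the data before it.

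**Off-drug safety follow-up is coherent.** Section 8.1 sets follow-up at 12 weeks after the last dose. Where withdrawal and last dose coincide, the three-month call gives a withdrawn patient about as much time off drug as week 24 gives a completer. This stands, and it is why the primary endpoint is not the target here.

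**The 100-day limit belongs mainly to the category.** A reader might infer that withdrawal alone makes the sustained class unreachable. It does not. The 84 treatment days are themselves below 100, and retained patients who start after day 68 also miss it. If the phrase means days on which alcohol was taken, a retained patient drinking 4 days a week for 24 weeks reaches only 4 × 24 = 96.

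**The contrast with section 4.4.2 is weak.** Permission is sought there because consent has gone; patients who still consent need none.

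**Conclusion.** The concern holds as a weakness in the secondary craving and relapse data, and a change is worth making. As written, the plan removes consenting patients from scheduled assessment for low adherence and for several drug-related reasons. One withdrawn just after week 4 loses the week 8 and week 12 urine tests and MELD-Na labs, and half of the PACS and MMSE contacts. The urine loss is 3 of 4 only if the table's week 24 mark is counted; by the prose it is 2 of 3.

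It would go too far to infer that the primary safety endpoint fails. All dosed patients are evaluated (section 7.3), adverse events before withdrawal are kept, and unresolved events are followed (sections 8.1 and 8.2). Later scheduled laboratory data are thinned, but that is a smaller matter.

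The direction of the selection is clear. Its size is not: the documents give no expected rate of withdrawal and no link between adherence and drinking. The 100-day result is only an illustration. It rests on elapsed days counted from enrolment and on a call at 84 to 92 days.

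**What to change.** - In sections 4.4.1 and 5.5, define stopping study drug and withdrawing from the study as separate events, and use each term for one of them only. The sponsor must reconcile the present wording and state what the adherence rule means for study drug. No drug-stopping rule is proposed here.
- Keep consenting patients who meet the adherence or drug-related grounds on the existing call, laboratory and urine schedule to week 24, as far as their condition allows.
- State that alcohol use and PACS collected after the drug is stopped are analysed, and report them apart from on-treatment data.
- Report each patient's length of follow-up beside the relapse category.

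The cost is protocol wording plus a few already-planned calls and tests in patients who are off drug. Completion, withdrawal and compliance issues are already source data under section 9.3.
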